##### **4.4.1 Adverse Events**

Adverse events are coded using the MedDRA dictionary and are categorized by system organ class (SOC) and preferred term (PT). Only treatment emergent adverse events are included in summary tabulations and include the following groupings: Double-Blind ATI-5002, Double-Blind Placebo, Open-Label ATI-5002 and Total ATI-50002 (Double-Blind + Open-Label). All adverse events are included in the data listings including those that are not considered treatment emergent.

To allow differentiation as to which study period an Adverse Event occurred, four categories are defined based upon onset date. Adverse Events that had onset dates prior to the first application of study medication are considered "prior". Adverse events with onset dates on or after the first application of double-blind study medication, prior to entry into open label (first application of open-label study medication) and within 30 days following the last application of study medication are considered "on double-blind therapy" or equivalently "treatment emergent". Events with onset dates on or after the first application of open-label study medication and within 30 days of the last application of study medication are considered "on-open-label therapy" and also considered "treatment emergent". Events with onset dates more than 30 days after the last application of study medication, be it double-blind or open label, are considered as "post-therapy".

Frequency tabulations are presented by MedDRA SOC and preferred term, for all adverse events; study treatment-related, adverse events resulting in discontinuation of study treatment, serious adverse events and adverse events by maximum severity. Adverse events resulting in discontinuation are those with 'action taken' recorded as 'drug withdrawn'.

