Study Design: During the double-blind period, this Phase 2, multicenter, randomized study is designed to evaluate the safety, tolerability, pharmacokinetics and pharmacodynamics of ATI-50002 Topical Solution in subjects with AU and AT. Subjects will be required to have a clinical diagnosis of stable, clinically typical, AU or AT for a duration of at least 6 months up to and including seven years. In the double-blind phase, a total of approximately 12 subjects will be randomized to a 2:1 ratio: 
 • ATI-50002 Topical Solution, 0.46%, BID for 28 days (8 subjects) • Vehicle Solution BID for 28 days (4 subjects) During the screening period, subjects will be assessed for eligibility into the study. Subjects who meet all the entry criteria will be randomized to ATI-50002 Topical Solution, 0.46% or Vehicle Topical Solution and will apply a minimum of 1.5 mLs up to a maximum of 4 mLs of study medication to the entire scalp twice-a-day (BID) for 28 days (except for Day 1 and Day 28 when study medication will only be applied once a day). For the first 6 subjects enrolled in the study, blood samples for concentrations of ATI-50002 will be collected on Day 1 (Visit 2) and Day 28 (Visit 6) at pre-dose and 1, 2, 4, 8 hours post dose and on Day 2 (Visit 3) and Day 29 (Visit 7) at 24 hours post-dose. Blood samples for immunology will be collected on Day 1 (Visit 2) before study medication application and on Day 29 (Visit 7), 24 hours after study medication application on Day 28 (Visit 6). A 4-mm punch biopsy of the scalp will be obtained to determine the concentration of ATI-50002 in the scalp skin on Day 2 (Visit 3) and on Day 29 (Visit 7) 24 hours after study medication application on Day 1 (Visit 2) and on Day 28 (Visit 6). A 4-mm punch biopsy will be obtained to determine histology and immunology, prior to study medication application on Day 1 (Visit 2) and on Day 29 (Visit 7), 24 hours after study medication application on Day 28 (Visit 6). Safety and tolerability will be evaluated	

at each study visit by assessment of adverse events and vital signs, and at select visits, ECGs and clinical laboratory tests will be completed.

Open-Label Extension:

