8.6. Dose Modification

Subjects should be instructed not to modify the study medication application procedure or frequency. All application modifications must be reported on the appropriate source document

and eCRF. If the subject experiences any significant application site AE(s), after discussion with the Sponsor, the investigator or designee may direct the subject to reduce study medication application frequency to once a day. Every effort should be made to resume twice daily applications for the week prior to Day 28 (Visit 6). If a subject cannot resume twice-daily applications to the scalp for more than 4 consecutive days, the subject must be removed from the study. Refer to Section 10.2.4 for Study Medication Interruption or Discontinuation due to related SAEs or specific abnormal laboratory values.

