12. STATISTICAL ANALYSES

12.1. Sample Size and Power Calculations

The planned sample size is 12 subjects. This is the first multicenter study evaluating the effect of ATI-50002 Topical Solution in subjects with stable alopecia universalis and alopecia totalis. No formal power calculations will be performed.

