On Day 29 (Visit 7) subjects who complete Visit 7, continue to meet the entry criteria and have no clinically significant AEs or tolerability issues will be eligible to enter a 12-month open-label extension. In the open-label extension, safety, tolerability and efficacy will be assessed. All subjects enrolled in the open-label extension will apply ATI-50002 Topical Solution, 0.46% to the entire scalp, twice daily for 52 weeks (12 months). In addition, subjects with eyebrow loss may apply a thin film of study medication to the affected eyebrow(s) twice-daily for 52 weeks (12 months). Subjects will be followed monthly for safety, tolerability and efficacy as detailed in Section [7.3](#). Subjects who decline or are not eligible for the open-label extension should be seen for suture removal, if applicable per Section 7.3 and Visit 16 (Post-treatment) 30 days  $\pm$  3 days following the Day 28 (Visit 6). Subjects enrolled in the initial 6-month Open Label Extension outlined by Protocol Amendment 1 (dated 06Feb2018) must be re-consented under Protocol Amendment 2 (dated 14AUG2018) in order to continue for an additional 6 months of Open Label treatment.

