#### **4.4.5 Laboratory Evaluations**

Shift tables showing changes in relationship to the normal reference range grade from baseline to the "worst" relationship recorded post-baseline are tabulated. In the event a patient had both "low" and "high" post-baseline values the patient will be counted under both "low" and "high". As such the percentages of the cells in the shift table may add to more than 100%.

Chemistry and Hematology parameters are summarized using descriptive statistics for each visit. Both actual values and changes from baseline are summarized.

The number and percentage of patients meeting criteria for hepatobiliary abnormalities and for potential renal impairment are provided for Double-Blind ATI-50002, Double-Blind Placebo, Open-Label ATI-50002 and Total ATI-50002 (Double-Blind + Open-Label).

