#### **4.7 Sample Size**

Since this is the first multicenter study of ATI-50002 Topical Solution in subjects with stable alopecia universalis and alopecia totalis, sample size considerations were based upon feasibility factors and not on a formal power computation.

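### The open-label safety column is not split by double-blind arm, so no summary table shows first exposure to ATI-50002 in former vehicle subjects

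*SAP*

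**What the plan says.** The Protocol Synopsis allocates 12 subjects 2:1: "ATI-50002 Topical Solution, 0.46%, BID for 28 days (8 subjects" and "Vehicle Solution BID for 28 days (4 subjects". Protocol 8.2 gives ATI-50002 to every subject in the extension, so former vehicle subjects start it there.

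SAP 2 makes completion of Visit 7 one condition of entry and then adds the rest: "continue to meet the entry criteria and have no clinically significant AEs or tolerability issues will be eligible to enter a 12-month open-label extension".

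SAP 4.4.1 assigns each adverse event to a study period by onset date and groups the summary tables as "Double-Blind ATI-5002, Double-Blind Placebo, Open-Label ATI-5002 and Total ATI-50002 (Double-Blind + Open-Label". SAP 4.4.5 repeats the grouping for the hepatobiliary and renal criteria: "Double-Blind ATI-50002, Double-Blind Placebo, Open-Label ATI-50002 and Total ATI-50002 (Double-Blind + Open-Label". Neither section divides the open-label column by earlier treatment.

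Three other places bear on the point:
- SAP 4 says that summaries are generally by double-blind group, and additionally for the subset entering open-label. It does not say whether open-label summaries are divided by earlier arm. It also sorts all listings by double-blind group and patient.
- SAP 4.4.1 puts every adverse event in the listings.
- SAP 4.3.2 summarises eyebrow scores at Visit 7 both by double-blind group and for all entrants together.

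**The concern.** Safety and tolerability belong to the primary objective, and SAP 4.8 drops the chi-square comparison of adverse event incidence. The descriptive columns are therefore the main safety output.

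The open-label column combines two groups in different positions. Former vehicle subjects are at the start of exposure. Former ATI-50002 subjects have had 28 days of it and passed an entry condition that, for them alone, screens on tolerance of the active drug. An event that tends to occur at first use would be counted mainly in the first group but divided by both. The percentage could then be read as the risk of starting treatment when it is something lower.

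The up to 4 former vehicle subjects are also the only first exposures outside the 8 randomised to ATI-50002. In a trial of 12 it is worth being able to see them in a table.

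**Working it through.** **Inputs.** From the documents: 12 subjects, 2:1 (Protocol 12.1 and Synopsis). Not given: the number entering the extension, any adverse event rate, any onset timing. Assumed, with ranges: p = risk at first use, q = risk in subjects already exposed.

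**Allocation.** 12 × 2/3 = 8 and 12 × 1/3 = 4, matching the Synopsis. SAP 4.7 says that "sample size considerations were based upon feasibility factors and not on a formal power computation", so there is no power figure to reproduce.

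**Open-label column if all 12 enter.** Expected rate = (4p + 8q)/12.

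| p | q | Column shows | Column ÷ p |
|---|---|---|---|
| 25% | 0% | 8.3% | 0.33 |
| 25% | 12.5% | 16.7% | 0.67 |
| 25% | 25% | 25.0% | 1.00 |
| 50% | 0% | 16.7% | 0.33 |
| 50% | 12.5% | 25.0% | 0.50 |
| 50% | 25% | 33.3% | 0.67 |

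The worst case (q = 0) is one third of p. When q = p there is no dilution.

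**Other entry patterns.** With q = 0 the column shows p times the share of first-time users. That share is 4/12 = 33% if all enter, 2/10 = 20% for 8 former ATI-50002 plus 2 former vehicle subjects, and 4/8 = 50% for 4 plus 4.

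**Strict selection at entry.** Suppose p = 30%, no later risk, every affected ATI-50002 subject stays out, and all 4 vehicle subjects enter. The column expects 4 × 0.3 = 1.2 subjects with events among 4 + 8 × 0.7 = 9.6, or 12.5%. The result is 7.7% if p = 20% and 18.2% if p = 40%.

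**The other two ATI-50002 columns, same assumptions (p = 30%).** Double-Blind ATI-50002: 2.4/8 = 30%. Total ATI-50002: (2.4 + 1.2)/12 = 30%. Both equal p. Once later events occur, Total adds them and no longer isolates the first 28 days.

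**Can the former vehicle count be recovered from the columns?** Not in general. Take 3 subjects with an event in Double-Blind ATI-50002, 2 in Open-Label and 5 in Total. Then the 2 open-label subjects are not among the first 3, but 0, 1 or 2 of them may be former vehicle subjects. The listings settle it; the tables do not.

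**What a split would show.** If 2 of 4 former vehicle and 0 of 8 former ATI-50002 subjects have an event, the pooled column reads 2/12 = 16.7% (exact 95% interval 2.1% to 48.4%). The split reads 2/4 = 50% (6.8% to 93.2%) and 0/8.

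**The case against.** The strongest reply is that little is hidden. All adverse events are listed, listings are sorted by double-blind arm, and at most 4 former vehicle subjects have to be read. The Double-Blind ATI-50002 column already shows first exposure in 8 randomised subjects, Total covers every first exposure, and the SAP nowhere presents the open-label column as the risk of starting treatment. All of this stands, and it limits the point to one column and to what the tables display.

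Several stronger readings are tempting but not supported:

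- A reader might infer that the first-exposure data are lost. They are in the listings.
- A reader might infer from Protocol 8.6 that application-site reactions are the main expected harm and come early. That section says only "If the subject experiences any significant application site AE(s), after discussion with the Sponsor" the application frequency may be reduced. It gives no rate, timing or ranking, so early onset is an assumption.
- A reader might credit a first-28-day table with raising the usable sample from 8 to 12, for example lowering the zero-event one-sided 95% upper bound from 31.2% to 22.1%. Total already covers up to 12 exposed subjects, and zero events there means zero at first exposure. The gain does not come from the new table.

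The strict-selection illustration is also an extreme. Entry turns on clinical significance as judged by the investigator (Protocol 4.1), so mild reactions need not bar it. Vehicle subjects face the same condition after 28 days on the same inactive ingredients (Protocol 8.1).

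Finally, SAP 4.4.1 may not be an exhaustive list, and SAP 4 defers detail to a data handling and programming document that is not available here. A split defined there cannot be excluded. If one exists, the SAP text should say so.

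**Conclusion.** The point holds as a minor one about presentation. The Open-Label ATI-50002 column in SAP 4.4.1 and 4.4.5 pools first-time users with subjects selected after 28 days on the drug. No named summary table shows first exposure in former vehicle subjects.

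If risk is higher at first use than later, the column understates the first-use rate, by up to about threefold with all 12 entering and no risk in prior users. With equal risks there is no understatement. The direction and size rest on assumed rates, since the documents give none.

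It would go too far to say that the plan dilutes early harm throughout. The randomised comparison with vehicle is unaffected, and the Double-Blind and Total ATI-50002 columns are not diluted by prior exposure. What remains is that Total does not separate the first 28 days from the following year.

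**What to change.** 1. In SAP 4.4.1 and 4.4.5, show Open-Label ATI-50002 by double-blind arm (former ATI-50002, former vehicle) as well as pooled.
2. In SAP 4.4.1 only, add one descriptive table of adverse events with onset within 28 days of each subject's own first ATI-50002 application. Show the double-blind ATI-50002 arm, the former vehicle subjects, and both combined (N up to 12). Do not extend it to laboratory criteria: in the schedule (Protocol 7.3) the first open-label laboratory sample is at Visit 9, OLE Day 56.
3. Footnote that the former vehicle part is open-label, selected at entry, and less closely observed. It has one scheduled visit in its first 28 days (OLE Day 28), whereas the double-blind period has contacts on Days 2, 8, 15, 27, 28 and 29.
4. SAP 4.6 and 4.8 are partly in the past tense. If outputs already exist, label the additions post hoc.

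The cost is some SAP wording, extra columns and one table. The onset and application dates are already needed for the period rules in SAP 4.4.1, and no trial procedure changes. The drawbacks are columns of at most 8 and 4 subjects and unequal ascertainment in the combined row, so the results stay descriptive.

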On Day 29 (Visit 7) subjects who complete Visit 7, continue to meet the entry criteria, have no clinically significant AEs or tolerability issues and in the opinion of the investigator have experienced or are capable of re-growing scalp hair will be eligible to enter a 12-month open-label extension. In the open-label extension, safety, tolerability and efficacy will be assessed. All subjects enrolled in the open-label extension will apply ATI-50002 Topical Solution, 0.46% to the entire scalp, twice daily for 52 weeks (12 months). In addition, subjects with eyebrow loss may apply a thin film of study medication to the affected eyebrow(s) twice-daily for 52 weeks (12 months). Subjects will be followed for safety, tolerability and efficacy as detailed in Section 7.3. Subjects who decline or are not eligible for the open-label extension should be seen for the Visit 16 (Post-treatment) assessments 30 days following the Day 28 (Visit 6). The duration of the open-label extension (OLE) should be based on the date of the visit that the subject initiated OLE treatment rather than the days from Baseline (Visit 2). For subjects who entered the open-label extension and had a gap between Visit 7 and entry into the open-label extension due to an administrative delay total study participation may be longer than 400 days.

Number of Subjects (planned):

12 subjects will be enrolled into the study.

Number of Study Sites:

This study will be conducted at two clinical sites.

Inclusion Criteria:

Subjects must meet all the following criteria to be eligible for participation in the study.

1. Able to comprehend and willing to sign an Informed Consent Form (ICF).
2. Male or non-pregnant, non-nursing female ≥ 18 years old at the time of informed consent.
3. Have a clinical diagnosis of stable, clinically typical, alopecia universalis or alopecia totalis.
4. Have a duration of the current episode of AU or AT for a minimum of 6 months and a maximum of seven years.
5. Have $> 95\%$ total scalp hair loss as measured by the Severity of Alopecia Tool (SALT).
6. If a woman of childbearing potential (WOCBP), must have a negative serum pregnancy test at Screening (Visit 1) and a negative urine pregnancy test (UPT) at Baseline (Visit 2) and agree to: use a highly effective method of birth control for the duration of the study; not be planning a pregnancy during the study duration and use contraception for 30 days after last application of study medication (Refer to Section 11).

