
16. Participation in an investigational drug or device trial in which administration of an investigational study drug or device occurred within 30 days or 5 half-lives (whichever is longer) of Screening (Visit 1). Subjects who have participated in a study of an investigational drug, device or biologic agent for alopecia areata (AA, AU or AT) within 1 year of screening will be eligible to participate only with individual permission from the Medical Monitor.
 
17. Sensitivity to any of the ingredients in the study medications.
 
18. History of or current alcohol or drug abuse within 2 years of assessment for study enrollment.
 
19. Screening ECG findings of:
 
 • QTcF >450msec for males or >470msec for females (use of the ECG algorithm is acceptable for this purpose) • Heart rate < 45 or > 100 beats/minutes (inclusive) • Rhythm disturbance other than sinus arrhythmia or ectopic supraventricular rhythm (ectopic atrial rhythm) • Conduction disturbance including PR >240msec, pre-excitation (delta wave and PR <120msec), second degree or higher AV block • Acute or chronic signs of ischemia • Left Bundle Branch Block • Prior myocardial infarction 		

Duration of Treatment
 
Double-blind Treatment
 
Screening period up to 30 days.
 
Double-blind treatment period is 29 days (maximum of 28 days of study medication application).
 
Post-treatment Visit 16 is up to 33 days (30 +3 days) following Day 29 for subjects not continuing into the open-label extension.
 
Total study participation for subjects from Baseline (Visit 2) through Post-treatment Visit 16(Day 59 + 3 days) is up to 62 days (29 + 33).
 
Double-Blind + Open-Label Extension
 
The duration of the total study participation from Baseline (Visit 2) to Week 56 (Visit 16) is anticipated to be a maximum of 400 days (393 + 7 days).
 
The duration of the open-label extension (OLE) should be based on the date of the visit that the subject initiated OLE treatment rather than the days from Baseline (Visit 2). For subjects who entered the open-label extension and had a gap between Visit 7 and entry into the open-label extension due to an administrative delay total study participation may be longer than 400 days.
		

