On Day 29 (Visit 7) subjects who complete Visit 7, continue to meet the entry criteria and have no clinically significant AEs or tolerability issues will be eligible to enter a 12-month open-label extension. In the open-label extension, safety, tolerability and efficacy will be assessed. All subjects enrolled in the open-label extension will apply ATI-50002 Topical Solution, 0.46% to the entire scalp, twice daily for 52 weeks (12 months). In addition, subjects with eyebrow loss may apply a thin film of study medication to the affected eyebrow(s) twice-daily for 52 weeks (12 months). Subjects will be followed for safety, tolerability and efficacy as detailed in Section 7.3. Subjects who decline or are not eligible for the open-label extension should be seen for suture removal, if applicable per Section 7.3 and Visit 16 (Post-treatment) 30 days \pm 3 days following the Day 28 (Visit 6). Subjects enrolled in the initial 6-month Open Label Extension outlined by Protocol Amendment 1 (dated 06Feb2018) must be re-consented under Protocol

Amendment 2 (dated 14AUG2018) in order to continue for an additional 6 months of Open Label treatment.

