⁹ Subjects must be instructed to apply the study medication according to the instructions in Appendix 1. Subjects will apply the first dose of study medication on the morning of Day 1 (Visit 2) and the last application of study medication on the morning of Day 28 (Visit 6), under the instruction and supervision of the study staff. Study medication at these visits should be applied in the morning to allow the 8-hour post dose assessments to occur at a reasonable time. On Day 1 (Visit 2) and Day 29 (Visit 7) subjects will only apply study medication once-a-day in the office.											
¹⁰ PK: A 4mm punch biopsy must be obtained on Day 2 (Visit 3) and Day 29 (Visit 7) 24 hours (± 30 minutes) after study medication application on Day 1 (Visit 2) and Day 28 (Visit 6).											
¹¹ PD: A 4mm punch biopsy must be obtained on Day 1 (Visit 2) before application of first dose of study medication and Day 29 (Visit 7) 24 hours (± 30 minutes) after study medication application. Subjects that choose to continue in to open-label extension treatment will also have a 4mm punch biopsy collected on Day 197 (Visit 13).											
¹² PK: The first 6 subjects enrolled in the study will have the blood PK testing performed. Blood for PK sampling will be obtained on Day 1 (Visit 2) and Day 28 (Visit 6), just prior to study medication application (predose), and 1, 2, 4, 8 hours post dose and on Day 2 (Visit 3) and Day 29 (Visit 7), 24 hours after study medication application (on Day 1 (Visit 2) and Day 28 (Visit 6). See Section 9.3.2 for PK sample draw time windows.											

	Open-Label Treatment										Post-Treatment ¹⁷
	Visit 8	Visit 9	Visit 10	Visit 11	Visit 12	Call	Visit 13	Optional Visit (Suture Removal)	Visit 14	Visit 15	
Week	8	12	16	20	24	28	28	30	40	52	56
Treatment Day ¹⁷	57 (OLE 28)	85 (OLE 56)	113 (OLE 84)	141 (OLE 112)	169 (OLE 140)	196 (OLE 167)	197 (OLE 168)	211 (OLE 182)	281 (OLE 252)	365 (OLE 336)	59/393 (OLE 364)
Treatment Window(days)	± 3	± 3	± 3	± 3	± 3	± 3	± 3	± 3	± 7	+7	± 3/± 7
¹³ Blood for immunology will be obtained prior to administration of study medication on Day 1 (Visit 2) and on Day 29 (Visit 7) 24 hours (± 30 min) after study medication application on Day 28 (Visit 6). Subjects that choose to continue in to open-label extension treatment will also have blood for immunology collected on Day 197 (Visit 13).											

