10.1.4. Adverse Event Reporting Period

The investigator must start reporting non-serious AEs with the subject's first study medication application and continue reporting until the end of the subject's last study visit. Reporting for SAEs must start when the subject signs the ICF and continue until the end of the subject's last visit.

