 On Day 29 (Visit 7) subject may be given the option to move into open-label extension treatment. 
 
• If the subject declines the open-label extension, she/he should be seen for the Visit 16 (Post-treatment) assessments 30 days following the date of Day 29 (Visit 7).
 
• If the subject chooses to continue in to the open-label extension, she/he must sign an ICF prior to being dispensed open-label drug and receiving continued study medication application instructions.
 
• If the subject enrolls in open-label treatment after Day 29 (Visit 7), an unscheduled visit will be conducted in order to obtain consent, review drug application instructions, and dispense drug. This will be considered the official date that the subject initiated open-label extension treatment and the scheduling of subsequent visits 8-16 should be based off of this date as referenced by (OLE xxx) in the treatment day schedule header above.
 
											
 Subjects who are eligible and consent to enter the open-label extension will have a baseline CEA and SEA completed at Visit 7 or the unscheduled Visit.											

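### SAP 4.4.1 counts double-blind adverse events over windows of about 28 to about 58 days depending on entry to the extension, so the two randomised columns may not be like-for-like

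*SAP*

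**What the plan says.** SAP 4.4.1 assigns each event to a period by onset date. An event is double-blind, and treatment-emergent, if its onset is on or after the first double-blind application, "prior to entry into open label (first application of open-label study medication) and within 30 days following the last application of study medication". The summary columns are double-blind active, double-blind placebo, open-label active and total active. They are frequency tables by system organ class (SOC) and preferred term (PT), with further tables for related events, discontinuations, serious events and maximum severity. The section gives no common cut-off day and no adjustment for length of observation.

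Entry to the extension is decided after randomisation. SAP section 2 requires Visit 7 to have been completed and adds these conditions: "continue to meet the entry criteria and have no clinically significant AEs or tolerability issues will be eligible to enter a 12-month open-label extension"; Protocol 7.1 has the same conditions. The protocol synopsis adds that subjects must "in the opinion of the investigator have experienced or are capable of re-growing scalp hair will be eligible". Subjects may also decline.

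Entry can be late. Footnote 17 of the schedule says: "If the subject enrolls in open-label treatment after Day 29 (Visit 7), an unscheduled visit will be conducted". The synopsis foresees subjects who "had a gap between Visit 7 and entry into the open-label extension due to an administrative delay", and gives no length for the gap.

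Events in the off-drug weeks are collected: Protocol 10.1.4 tells investigators to "continue reporting until the end of the subject's last study visit", and non-entrants return for Visit 16 about a month after dosing ends.

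**The concern.** The number of days over which a subject can contribute a double-blind event is not fixed by design. It depends on whether and when that subject starts open-label drug, which in turn depends partly on how treatment was tolerated. The outcome being compared therefore influences how long it is observed.

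Safety and tolerability against vehicle belong to the primary objective (SAP 1.1), and the two double-blind columns are the only randomised safety contrast in the trial. If one arm has more non-entrants, or more delayed entrants, its column gathers events over more off-drug time.

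A concrete case: PK and PD scalp biopsies are taken on Day 29. A wound event on Day 33 goes into the double-blind column for a non-entrant. For a subject who began open-label drug on Day 29, the same event goes into the open-label column.

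**Working it through.** **Figures in the documents.** The documents state no length in days for the TEAE window. The nearest stated figure is the maximum participation of a non-entrant, 62 days, which reproduces: 29 + 33 = 62 and 59 + 3 = 62. Twelve subjects at 2:1 give 8 and 4.

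**Window length.** The last double-blind application is on Day 28 (schedule, footnote 9). From SAP 4.4.1:

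last counted day = min(day of first open-label application − 1, day of last double-blind application + 30)

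- Open-label starts on Day 29: min(28, 58) = 28 days.
- Open-label starts on Day 43 after a gap: min(42, 58) = 42 days.
- Open-label starts on Day 59 or later: 58 days.
- Never enters, last application Day 28: 58 days.
- Never enters, last application Day 25 (Visit 6 has a −3 day window): 25 + 30 = 55 days.

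The largest ratio is 58/28 = 2.07. For non-entrants, collection ends at Visit 16. Depending on the passage, that is 30 ± 3 days after Day 28 (Days 55 to 61) or after Day 29 (Days 56 to 62), so nearly all of the window is observed.

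**Illustration.** The rates and the entry split are assumptions; the documents give neither. Take a constant hazard, equal in both arms, and non-entry unrelated to adverse events, with 3 of 8 active and 0 of 4 vehicle subjects not entering. All entrants start on Day 29.

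p58 = 1 − (1 − p28)^(58/28); active column = (3 × p58 + 5 × p28)/8; vehicle column = p28.

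| p28 (assumed) | p58 | Active column | Vehicle column | Artefact (points) |
|---|---|---|---|---|
| 10% | 19.6% | 13.6% | 10% | 3.6 |
| 20% | 37.0% | 26.4% | 20% | 6.4 |
| 30% | 52.2% | 38.3% | 30% | 8.3 |
| 50% | 76.2% | 59.8% | 50% | 9.8 |

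If entry shares and timing are equal in the two arms, both columns rise together and the artefact is 0. If the split is reversed, so is its sign.

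**Which tables are affected.** Suppose instead that non-entry is caused only by a TEAE in Days 1 to 28. That subject already counts as having any TEAE, and the extra 30 days cannot change this. The any-TEAE proportion is unaffected. A different PT, unrelated to the event that barred entry, still has 30 more days in which to appear. With p28 = 20% for that PT and non-entry of 50% versus 0%, the columns read 0.5 × 37.0% + 0.5 × 20% = 28.5% versus 20.0%. Relatedness and maximum-severity counts can rise in the same way.

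**The case against.** A reader might infer three stronger claims that the documents do not support.

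- *Entry requires having had no adverse events.* The rule is no clinically significant events or tolerability issues, so subjects with other events may enter.
- *Entrants have 28 days and non-entrants 58.* Delayed entrants fall anywhere from 28 to 58 days. A non-entrant who stops early has fewer than 58, because the 30 days run from that subject's last application. Subjects stopped for intolerance will often be in this group.
- *The longer window goes to subjects with events and so creates a difference in overall incidence.* As shown above, a subject barred by a TEAE is already counted. The 26% versus 20% figure needs non-entry for other reasons.

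It can also be argued that, if the treatments truly do not differ, randomisation and blinding make entry balanced in expectation, so a 3/8 versus 0/4 split would be chance. If the split reflects worse tolerability, a real difference exists and the rule amplifies it. This is correct for the average over repeated trials and for the event that bars entry. It does not protect a single table of 8 and 4 subjects, nor PTs that have nothing to do with the reason for non-entry.

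Finally, the comparison is descriptive. SAP 4.8 drops the chi-square test, all events are listed, and a 6.4-point artefact is about half a subject in an arm of 8 (one subject is 12.5 points; in the vehicle arm, 25). That limits the consequence. It also leaves readers with raw proportions only, so the proportions should cover the same period. A separate data-handling specification, not among the documents reviewed, might add rules, but SAP 4.4.1 already states the classification explicitly.

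**Conclusion.** The concern holds in a limited form. SAP 4.4.1 gives double-blind windows of about 28 days (entry at Visit 7), 28 to 58 days (entry after a gap) and up to about 58 days (Day 28 completers who do not enter), and window length depends on events after randomisation. The arm columns are distorted only if entry shares or timing differ between arms, through chance or tolerability. Non-entry caused by adverse events then affects SOC, PT, relatedness and severity counts; non-entry for other reasons, and gaps, also affect the any-TEAE proportion.

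In the illustration the artefact is 3.6 to 9.8 points for assumed 28-day risks of 10% to 50%. That range rests on equal constant hazards, non-entry unrelated to adverse events and an assumed 3/8 versus 0/4 split, and it is zero when entry shares and timing match. No formal test is affected. The change is worth making because it is cheap and this is the only randomised safety contrast.

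**What to change.** In SAP 4.4.1:

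1. For the double-blind columns, count events with onset from the first double-blind application through Day 29 or until the first open-label application, whichever is earlier, in every subject.
2. Put later events, with onset before any open-label application and within 30 days of the last application, in a separate row labelled post-double-blind follow-up, by randomised arm.
3. State that follow-up events in subjects randomised to ATI-50002 remain in the Total ATI-50002 column.

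The cap at first open-label application is needed because open-label drug can be dispensed at Visit 7, which is Day 29 with a −3 day window. A fixed Day 29 cut-off alone could place a vehicle subject's first reaction to active drug under vehicle. The cap leaves a small inequality: 28 versus 29 days when open-label starts on Day 29, and up to four days if it starts on Day 26 (25 versus 29). In the 20% illustration with a Day 29 start, 1 − 0.8^(29/28) = 20.6%, and the active column becomes (3 × 20.6% + 5 × 20%)/8 = 20.2% versus 20%.

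The cost is one revised definition, one extra row and one sentence on the total column, with no new data. The small downside is that delayed events leave the main double-blind column, but they stay tabulated and listed. Two sets of passages should also be reconciled: the timing of Visit 16 for non-entrants (counted from Day 28 or from Day 29), and the entry conditions in the synopsis against those in Protocol 7.1 and SAP section 2.
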